2.2.3. Additional Estimands

Not applicable.

2.3. Study Design

Study C3731003 is a Phase 3, open-label, multicenter, single arm study to evaluate the efficacy and safety of a single infusion of PF-07055480 in adult male participants with moderately severe to severe hemophilia A (FVIII:C \leq 1%).

Eligible study participants will be followed while on routine FVIII prophylaxis therapy in the lead-in Study C0371004 in order to collect pretreatment (established usual care) data for efficacy and selected safety parameters.

This study will include an approximately 6-week screening (screening can be extended beyond 6 weeks when needed) and baseline period followed by the dosing day (Day 1), a 2-year efficacy and safety observation period (short term monitoring), and a 3-year long-term monitoring period.

This study will enroll approximately 70 eligible participants from Study C0371004 to achieve at least 50 dosed participants who complete at least 15 months of follow-up postinfusion in this study (C3731003). These 50 participants will have completed at least 6 months of routine prophylaxis follow up in Study C0371004. The duration of follow up for subsequent participants in the lead-in study (C0371004) may be shorter than 6 months after at least 50 hemophilia A participants are expected to reach 15 months postinfusion in this study (C3731003). The study design is displayed in [Figure 1](#) below.

[figure not shown]
The primary analysis will be conducted when at least 50 dosed participants have reached at least 15 months of follow-up postinfusion, corresponding to at least 12 months of follow-up for these 50 dosed participants after the estimated FVIII activity steady state onset. The onset of FVIII activity steady state based on the C3731001 study data is expected to be reached at the beginning of Week 9 postinfusion. However, as a conservative approach, the beginning of steady state will be considered as Week 12 (i.e., approximately 3 months) for the primary analysis.

A final analysis will be conducted when all dosed participants have completed the entire study (i.e., 5 years in follow-up duration per participant) or discontinued prematurely from the study.

The study may be paused in the event of a confirmed inhibitor level or a thrombotic event suspected to be related to $>$ upper limit of normal (ULN) for FVIII activity levels for a participant as described in the Protocol Sections 8.1.2.3 and 8.2.6.2.

If the decision to pause the study is made, no additional participant will be treated until the circumstances for such an event are assessed and regulatory agencies are notified, if required. If paused, the trial re-start will only be possible after Regulatory Authority approval via substantial amendment, where applicable based on local/regional regulatory requirements.

Figure 1. C3731003: Study Design

3. ENDPOINTS AND BASELINE VARIABLES: DEFINITIONS AND CONVENTIONS

3.1. Primary Endpoint

The primary efficacy endpoint will be the Total ABR (including both treated and untreated bleeds) from Week 12 [Day 78] through at least 15 months of follow up, following infusion of PF-07055480 versus Total ABR while on FVIII prophylaxis replacement regimen prior to infusion of PF-07055480.

3.1.1. Total Annualized Bleeding Rate (Total ABR)

An eDiary, a handheld device, will be provided to all participants on Visit 1. Participants are required to enter any occurrence of hemophilic bleeding episodes (including date, time,

location, and etiology) and any exogenous FVIII replacement (including date, time, reason, and dose) required to treat the bleeds in the eDiary.

Definitions of bleeds are provided below.

Treated Bleed: An event necessitating administration of coagulation factor within 72 hours of signs or symptoms of bleeding (protocol definition, unless specifically referring to untreated bleed).

Untreated Bleed: A bleeding event not necessitating administration of coagulation factor within 72 hours of signs and symptoms of bleeding.

New Bleed:

- A ‘new treated bleed’ is a bleed necessitating treatment (as described above) occurring >72 hours after stopping treatment from the original bleed for which treatment was initiated or a bleed necessitating treatment (as described above) occurring at a different site from the original bleed regardless of the time from last injection.
- A bleed is considered a ‘new untreated bleed’ if it does not necessitate treatment and occurring >72 hours after the previous untreated bleed at the same site or occurring >72 hours after stopping treatment from the original bleed for which treatment was initiated, or an untreated bleed occurring at a different site from the original bleed regardless of the time from last bleed or last injection.

If a bleed is treated with FVIII infusion (as indicated in the bleeding log of the eDiary) within 72 hours (by comparing date/time of bleeding to date/time of infusion in the eDiary), regardless of the type of treatment (preventive, prophylaxis or on demand), it will be considered as a treated bleed. If a bleed is not treated with FVIII infusion, as indicated in the eDiary bleeding log, the bleed will be considered as an untreated bleed. Table 6 provides a summary of bleeds that are considered treated/untreated bleeding events based on the data captured within the eDiary.

Table 6. Treated Bleeds / Untreated Bleeds Based on eDiary Data

Factor infusion was used to treat the bleed? (reported in eDiary bleeding log)	Any FVIII infusion within (\leq) 72 hours post bleeding?	Treated/Untreated bleed
Yes	Yes (regardless of reason)	Treated bleed
Yes	No	Untreated bleed
No	Yes (regardless of reason)	Untreated bleed
No	No	Untreated bleed

Only new bleeds will be counted toward the number of bleeds for ABR calculation. New bleeds that occurred on the same date will be counted using the following algorithm to derive overall bleeds and bleeds by location type as displayed in [Table 7](#) below.

Table 7. Counting New Bleeds Occurring on the Same Date Based on Bleeding Time, Location Type, And Bleeding Site

Multiple new bleeding episodes occurring (regardless spontaneous or traumatic) on the same date	Same location type	Same bleeding site*	Counting toward overall bleeds	Counting toward bleeds by location type
Same date/time	Yes	No	One bleeding episode	One bleeding episode at the given location type
Same date/time	No	No	One bleeding episode	One bleeding episode for each location type
Same date but different time	Yes	No	Separate bleeding episodes	Separate bleeding episodes at the given location type
Same date but different time	No	No	Separate bleeding episodes	One bleeding episode for each location type

Note: Location type refers to joint and soft tissue/muscle/other. Bleeding site refers to the body location (e.g., left/right shoulder, left/right knee, left/right arm, etc.).

*Per the definition of new bleeds, there won't be multiple new bleeds occurring at the same bleeding sites on the same date.

The number of treated and untreated bleeding episodes from Week 12 [Day 78] through data cutoff (at least 15 months) after PF-07055480 infusion will contribute to the postinfusion Total ABR calculation of each participant, which is considered the primary endpoint. Total ABR during additional time periods postinfusion (as indicated below) will be analyzed as secondary endpoints. The following yearly intervals as well as cumulative follow-up intervals will be used for reporting Total ABR data postinfusion. Note: here and throughout, Year 2 summaries include data following Month 15 (Day 455) through Month 24 (Day 730).

Yearly Interval	Interval Derivation
Month 15	Day 77 < Month 15 ≤ Day 455
Year 2	Day 455 < Year 2 ≤ Day 730
Year 3	Day 730 < Year 3 ≤ Day 1095
Year 4	Day 1095 < Year 4 ≤ Day 1460
Year 5	Day 1460 < Year 5

Note: Day 1 is the day when PF-07055480 infusion started.

Cumulative follow-up interval	Interval Derivation
Cumulative follow up through 2 years postinfusion	Day 78 to Day 730
Cumulative follow up through 3 years postinfusion	Day 78 to Day 1095
Cumulative follow up through 4 years postinfusion	Day 78 to Day 1460
Cumulative follow up through 5 years postinfusion	Day 78 to End of the study

For participants with incomplete data for the entire yearly time period, including participants who discontinued, all data during the specified period will be annualized and summarized utilizing the number of days of follow-up during the given time period (i.e., observation period). Total ABR for each participant will be calculated as below:

Total ABR =

$$\frac{(\text{Number of treated and untreated bleeding episodes during the given time period}) \times 365.25}{(\text{Number of days of follow-up in the given time period})}$$

Data before Week 12 postinfusion are excluded to account for the potential differences in participants' pharmacokinetics postinfusion. As a result, the denominator in the above calculation for the Month 15 and cumulative follow-up intervals will be [the last date in the given time period – (Date of PF-07055480 infusion) – 77 days +1].

For the primary endpoint assessment of Total ABR from Week 12 through at least 15 months (up to data cutoff), the number of bleeds post resumption of prophylaxis regimen or study discontinuation will be excluded. As a result, the denominator (i.e., number of days in the observation period) in the above Total ABR calculation will include days up to data cutoff, the day before resumption of prophylaxis regimen, or discontinuation date, whichever occurs earliest.

Total ABR during yearly intervals and cumulative follow-up intervals are considered as secondary endpoints. If the participant discontinues from study before the end of the prespecified observation period, the last date in the given observation period will be the date of study discontinuation. In addition, if FVIII prophylaxis regimen is resumed for a participant as defined in Protocol Section 6.5.1 then data collected on and after the date of prophylaxis resumption entered in the eCRF by the investigator will be excluded from the calculation of Total ABR by interval, which means the bleeding events will be excluded and the corresponding time period will be deducted as well.

Total ABR prior to PF-07055480 will be calculated using all treated and untreated bleeds documented during the lead-in study (C0371004) up to preinfusion of PF-07055480 and the respective number of days of follow-up within the lead-in study and preinfusion period using the same formula presented above.

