
	HAVEN1 (Inhibitors)			HAVEN3 (No inhibitors)		
	Prophylaxis	On demand	Treatment difference	Prophylaxis	On demand	Treatment difference*
Treated ABR	2.9	23.3	20.4	1.5	38.2	36.7
Total ABR	5.5	28.3	22.8	2.5	47.6	45.1
Ratio (Total/Treated)	1.90		1.12	1.67		1.23

*Difference between the on-demand treatment and the emicizumab prophylaxis in the once weekly group.

Adjustment of M1 and M2 :

M1 of 16.8 (difference in mean treated ABR between FVIII product prophylaxis and on-demand treatment based on internal studies listed above) is expected to be equivalent to 19.66 (ie, 16.8×1.17) when considering mean Total ABR. Preservation levels of 75%, 80%, and 85% of M1 will correspond to noninferiority margin values of 4.9, 3.9, and 2.9 bleeding events/year, on an absolute scale, respectively. A value of 3.0 for M2 (approximately 84.7% of the M1 effect preserved) is both clinically meaningful and yielding a reasonable sample size for establishing efficacy based on Total ABR.

Adjustment of assumptions:

According to Table 3, the ratio of Total ABR over treated ABR in the emicizumab prophylaxis treatment group was 1.90 in the HAVEN1 study and 1.67 in the HAVEN3 study. It is assumed that the relationship between Total ABR and treated ABR with gene therapy is similar to that with emicizumab prophylaxis therapy.

Study C3731003 assumes the treated ABR under the standard FVIII prophylaxis regimen is 4 bleeds/year based on related data in 3 internal studies and 1 bleed/year (a 75% reduction from 4 bleeds/year) with the gene therapy. Based on the ratio of 1.90 for Total ABR over treated ABR from HAVEN1 (ie, the higher ratio of Total/Treated observed), it is assumed the Total ABR will be 2 bleeds/year after the gene therapy (ie, $1 * 1.90$ approximately equal to 2). In addition, the lowest mean treated ABR reported among the 3 internal FVIII product studies was 2.6; as a conservative approach, Total ABR will be assumed to correspond to 5 bleeds/year (ie, $2.6 * 1.90$ approximately equal to 5) for prior prophylaxis treatment. This assumption is equivalent to a 60% reduction in mean Total ABR after gene therapy compared to prophylaxis treatment.

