Based on the simulations described above, the sample size for the primary analysis based on Total ABR remains unchanged. A sample size of at least 50 dosed participants who have completed at least 15 months of follow-up post PF-07055480 infusion will provide at least 95% power (1-sided test with alpha=0.025) to demonstrate noninferiority of gene therapy compared to prophylaxis treatment based on a difference in mean Total ABR with an NI margin of 3.0 bleeds/year.

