10.7. Appendix 7: Factor Replacement Regimens and Bleed Definitions

Definition of Factor Replacement Regimens

Prophylaxis Therapy: The regularly scheduled and regimented administration of factor replacement therapy to prevent bleeding.

Preventative Therapy: Infusion of clotting factor that is given in anticipation of a planned physical activity that has a high risk of injury (eg, surgery or sporting activity).

On-Demand Therapy: The administration of factor replacement therapy only at the time of an acute bleeding event.

Definition of a Bleed

Treated Bleed: An event necessitating administration of coagulation factor within 72 hours of signs or symptoms of bleeding (protocol definition, unless specifically referring to untreated bleed).

Untreated Bleed: A bleeding event not necessitating administration of coagulation factor within 72 hours of signs and symptoms of bleeding.

New Bleed: A bleed occurring >72 hours after stopping treatment from the original bleed for which treatment was initiated or a bleed occurring at a different site from the original bleed regardless of the time from last injection.

Definition of a Bleed Location

Target Joint: Defined as a major joint (eg, hip, elbow, wrist, shoulder, knee, and ankle) into which repeated bleeds occur (3 or more spontaneous bleeds into a single joint within a consecutive 6-month period). A target joint is considered resolved when there are ≤ 2 bleeds into the joint within a 12-month period.

Joint Bleed: A bleeding episode characterized by rapid loss of range of motion as compared with baseline that is associated with any combination of the following: pain or an unusual sensation in the joint, palpable swelling, and warmth of the skin over the joint.

Muscle Bleed: An episode of bleeding into a muscle, determined clinically and/or by imaging studies, generally associated with pain and/or swelling and functional impairment.

Definition of Bleed Types

Spontaneous Bleeds: Bleeding for no apparent/known reason particularly into the joints, muscles, and soft tissues.

Traumatic Bleeds: Bleeding event occurring for an apparent/known reason.

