5. GENERAL METHODOLOGY AND CONVENTIONS

The primary analysis will be conducted when at least 50 dosed participants have completed at least 15 months of follow up post PF-07055480 infusion. The primary analysis is focused on the efficacy and safety during the follow-up through data cutoff postinfusion. The associated efficacy endpoints and analysis methods are listed in the tables below. The final analysis will be conducted when all dosed participants have completed the entire study (i.e., 5 years in follow-up duration per participant) or discontinued prematurely from the study. The planned endpoints after the primary analysis are focused on extended efficacy and longer-term safety. As this is an open-label study, the sponsor may conduct reviews of the data during the course of the study for the purpose of safety assessments. There may be several periodic reviews of data between the primary analysis and the final analysis for the purpose of publications and regulatory updates, etc.

Category of Endpoint	Primary Analysis Endpoints And Statistical Analysis Methods
Primary	Total ABR (treated and untreated bleedings) from Week 12 [Day 78] through at least 15 months (up to data cutoff) postinfusion of PF-07055480 will be compared to preinfusion

Category of Endpoint	Primary Analysis Endpoints And Statistical Analysis Methods
	of PF-07055480 (under SOC FVIII prophylaxis replacement regimen). A repeated measures negative binomial regression model will be used to test NI with NI margin = 3 bleeds/year at the one-sided alpha level = 0.025. If noninferiority is demonstrated, further testing for superiority would be conducted.
Key secondary	
 FVIII activity level > 5% at 15 months postinfusion of PF-07055480. The percentage of participants will be compared to a null hypothesis of percentage $\leq 68\%$ using an exact binomial test at the one-sided alpha level = 0.025. Based on the interim data of the Phase 1b/2 Study, 80% of participants in Cohort 4 (Phase 3 study dose) had a FVIII activity level greater than 5% at 18 months postinfusion. The null hypothesis of percentage $\leq 68\%$ will be rejected if the observed percentage is greater than 80%. Treated ABR from Week 12 [Day 78] through at least 15 months (up to data cutoff) post PF07055480 infusion will be analyzed separately using the same method as applied to Total ABR.

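### The new-bleed rules in SAP 3.1.1 can count one episode twice in Total ABR and do not deliver the one-new-bleed-per-site-per-date property that the Table 7 footnote claims for them

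*SAP*

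**What the plan says.** - **New untreated bleed (SAP 3.1.1).** An untreated bleed is new if it is "occurring >72 hours after the previous untreated bleed at the same site or occurring >72 hours after stopping treatment from the original bleed", or if it is at a different site from the original bleed.
- **New treated bleed (SAP 3.1.1).** A treated bleed is new if it comes more than 72 hours after treatment of the original bleed stopped, or is at a different site. Earlier untreated bleeding is not mentioned.
- **Classification (SAP Table 6).** An entry logged as not treated with factor stays untreated even when an infusion follows within 72 hours for any reason.
- **Counting (SAP 3.1.1, Table 7).** "Only new bleeds will be counted toward the number of bleeds for ABR calculation". Every row of Table 7 concerns bleeds at different sites. The footnote explains why: "Per the definition of new bleeds, there won't be multiple new bleeds occurring at the same bleeding sites on the same date".
- **Protocol Appendix 7.** There is one rule for a new bleed: "A bleed occurring >72 hours after stopping treatment from the original bleed for which treatment was initiated", or a bleed at a different site. It has no separate rule for untreated bleeds.
- **Both periods.** Preinfusion Total ABR "will be calculated using all treated and untreated bleeds documented during the lead-in study (C0371004) up to preinfusion of PF-07055480", with the same formula as after infusion.
- **Use.** Total ABR is steps 1 and 7 of the gatekeeping sequence (SAP Table 8). The primary model is used "to test NI with NI margin = 3 bleeds/year at the one-sided alpha level = 0.025".
- **Sensitivity analyses (SAP 6.1.1.2).** These vary the population and the preinfusion data window. None varies the new-bleed definition.

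**The concern.** The purpose of a new-bleed rule is to stop one episode being counted twice when the diary holds several entries for it. That requires each entry to be checked against both earlier treated and earlier untreated bleeding at the same site. The treated rule checks only one of these. The untreated rule names both but joins them with 'or', so on a literal reading satisfying either one is enough. The footnote under Table 7 relies on a property that the definitions do not guarantee, and Table 7 gives a programmer no row for the same-site case.

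The stake is the primary endpoint of an open-label before/after comparison based on diary entries. Every miscount adds a bleed and none removes one. Unless it is equal in the two periods, it moves the estimated difference, and it distorts the reported rates in any case. No planned analysis would show the effect.

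**Working it through.** **1. The plan's own figure.** Protocol 9.2 states at least 95% power with 50 participants.

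Inputs from the documents: Total ABR 5 before (2.6 × 1.90 = 4.94) and 2 after infusion (1 × 1.90 = 1.9); correlation 0.2; margin 3; one-sided 0.025; at least 6 months before infusion (0.5 y); Day 78 to Day 455 after it (455 − 77 = 378 days, 1.035 y). The dispersion k is not given.

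Normal approximation for a paired rate difference:

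v = μ/t + kμ²; SE = √[(v₀ + v₁ − 2 × 0.2 × √(v₀v₁))/50]; power = Φ((3 − (2 − 5))/SE − 1.96)

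At k = 5: v₀ = 5/0.5 + 5 × 25 = 135; v₁ = 2/1.035 + 5 × 4 = 21.93; SE = √(135.17/50) = 1.644; power = Φ(6/1.644 − 1.96) = 95.4%. Power is 98.1% at k = 4 and 91.8% at k = 6. The stated figure therefore reproduces for k up to about 5. The planned difference (−3) lies 6 bleeds/year from the margin (+3).

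**2. The rules applied to short records at one site.**

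| Record | Literal 'or' | Case-by-case reading | Two-way look-back |
|---|---|---|---|
| A: treated Day 50, treatment stops Day 51; untreated Day 100; untreated Day 102 | 3 | 2 | 2 |
| B: untreated Day 90; treated Day 100, stops Day 101; untreated Day 102 | 3 | 2 | 2 |
| C: untreated Day 100; treated Day 101 | 2 | 2 | 1 |
| C reversed: treated Day 100, stops that day; untreated Day 101; no older untreated bleed | 1 | 1 | 1 |

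- In A, the Day 102 entry is 48 hours after an untreated bleed but 51 days after treatment stopped, so the second clause makes it new.
- In B, it is 24 hours after treatment stopped but 12 days after the last untreated bleed, so the first clause makes it new.
- In C, Table 6 keeps the first entry untreated, and the treated rule has no earlier treatment to look back to. Both entries are new under either reading of the 'or'. If both fall on one date, the result is two new bleeds at one site on one date, which the footnote says cannot happen.

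A related gap is that the original bleed is not defined. If a knee bleed is the original, a second elbow entry hours after a first elbow entry is still at a different site from it.

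**3. Size of the 'or' fault.** Diary entries were simulated for 15,000 participants per setting. Rates follow the plan: treated/untreated 2.6/2.4 per year before (5 − 2.6 = 2.4) and 1/1 after, over 0.5 y and 1.035 y. Four things are assumed, because the documents do not give them:
- the share of bleeds followed by a repeat untreated entry within 72 hours at the same site (10% or 30%);
- the number of bleeding sites (1, 3 or 6, equally likely);
- dispersion 1;
- whether the look-back restarts at infusion or spans all history.

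Extra bleeds/year, literal 'or' minus both conditions required (shifts computed before rounding):

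| Look-back | Sites | Repeat share | Before | After | Shift in difference |
|---|---|---|---|---|---|
| Restarts | 1 | 10% | 0.393 | 0.120 | −0.273 |
| Restarts | 1 | 30% | 0.938 | 0.329 | −0.610 |
| Restarts | 3 | 10% | 0.180 | 0.057 | −0.124 |
| Restarts | 3 | 30% | 0.491 | 0.175 | −0.316 |
| Restarts | 6 | 10% | 0.094 | 0.030 | −0.063 |
| Restarts | 6 | 30% | 0.295 | 0.099 | −0.197 |
| All history | 1 | 10% | 0.378 | 0.199 | −0.179 |
| All history | 1 | 30% | 0.912 | 0.546 | −0.366 |
| All history | 3 | 10% | 0.177 | 0.130 | −0.047 |
| All history | 3 | 30% | 0.516 | 0.401 | −0.115 |
| All history | 6 | 10% | 0.091 | 0.087 | −0.004 |
| All history | 6 | 30% | 0.291 | 0.270 | −0.020 |

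The largest shift, 0.61, is about 10% of the 6 bleeds/year to the margin (0.61/6). The fault in Record C was not simulated, so no size is given for it.

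**4. Ratio scale.** The planned reduction is 1 − 2/5 = 60%. Adding the all-history, one-site, 30% figures gives 1 − 2.546/5.912 = 56.9%. With a restarting look-back the same setting gives 1 − 2.329/5.938 = 60.8%. The direction on this scale therefore depends on the unstated look-back.

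**The case against.** **The 'or' can be read by case.** If the last bleed at the site was untreated, use the first clock; if it was treated, use the second. Under that reading Records A and B each give 2. The footnote to Table 7 supports this intent, because it cannot be true under a free 'or'. This stands. A reader might infer that the SAP will count A and B as three bleeds each, but the documents show only that the wording permits it. It does not answer Record C, which fails under both readings.

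**Record C follows Protocol Appendix 7 and needs one episode entered twice.** Protocol 8.1.1 also has the site review bleeds and related treatments with the participant for consistency. That review may make such records less frequent, and the documents give no rate for them. But the derivation has no step that merges the entries, and agreement with the protocol wording does not make the SAP footnote true.

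**The bias falls mainly on the comparator.** A reader might infer this because bleeding is more frequent before infusion. It holds if the look-back restarts at infusion, when 74–77% of the added rate is preinfusion. If all history counts, the share is 51–66% and the relative inflation is larger after infusion (4–27% against 2–18%). The documents do not say which applies.

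**Merging a treated entry with an earlier untreated one conflicts with Table 6.** It would if the untreated entry were relabelled as treated. It does not if only the count changes.

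**Conclusion.** The new-bleed rules do not deliver what the Table 7 footnote says of them. The one-way look-back in the treated rule is a definite gap. The 'or' is an ambiguity that conflicts with the SAP's own footnote, not a proven counting error. Either fault can only raise the Total ABR count. Neither one changes Treated ABR (steps 3 and 6), since the treated entry counts once either way.

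On the difference scale used for the primary test, the 'or' fault moved the result by about 0 to −0.6 bleeds/year, in no tested setting against the gene therapy. These sizes rest on assumed repeat-entry shares, site numbers and dispersion, and on a paired-difference approximation instead of the planned GEE model. A reader might infer that the fault could produce a false noninferiority finding. The figures do not support that: under the planning assumptions it is not enough by itself to decide the test. The correction is still worth making because it is cheap and concerns how the primary endpoint is counted.

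**What to change.** Rewrite the new-bleed definitions in SAP 3.1.1:

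- **Untreated bleed, same site:** new only if it is more than 72 hours after the previous untreated bleed at that site (if any) **and** more than 72 hours after treatment stopped for any earlier treated bleed at that site (if any).
- **Treated bleed within 72 hours of an untreated entry at the same site:** one episode in Total ABR. Keep the treated entry and do not count the earlier untreated entry separately. Leave the Table 6 classification of each entry unchanged.
- **Different site:** judge it against every bleed in the look-back, not against one original bleed. Where this applies to treated bleeds it can also affect Treated ABR.
- **Look-back:** state whether it spans infusion.
- **Application:** use the identical rule for lead-in and postinfusion data.

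The Table 7 footnote then follows from the definitions.

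Cost: a short SAP edit, one derivation program, and alignment of the Protocol Appendix 7 wording. SAP Section 2 says major modifications of the primary endpoint definition also go into a protocol amendment, so the sponsor should decide whether this edit counts as one.
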